# 6.4 Study Stopping Rules

This is a phase I trial with a 3+3 study design. Subjects will be monitored for DLTs lasting no later than Day 56; however, if all patients in a dose cohort have recovered from DLTs prior to Day 56, dose escalation may proceed. If a DLT occurs in 1 of the 3 subjects in a given dose cohort, the dose cohort will be expanded to 6 subjects. If 2 of the total 6 subjects in any given dose cohort

experience a DLT, the next lower dose level will be explored and considered the maximum tolerated dose (MTD), if no more than 1 of 6 subjects experience a DLT. If this occurs in cohort 1, the dose will be decreased to cohort -1 and if 2 or more DLTs are reached in dose level -1, the study will be put on hold and a protocol amendment will be considered.

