# 5.1 Dose Escalation Rules

- Three to six subjects will initially be enrolled at dose level 1. If none of the 3 subjects experience a dose limiting toxicity (DLT) during the first cycle of therapy, an additional three subjects will be enrolled at dose level 2. If none of the 3 subjects at dose level 2 experience a dose limiting toxicity (DLT), an additional three subjects will be enrolled at dose level 3. If all subjects in dose level 3 complete the first cycle of therapy without DLT, 3 more subjects will be enrolled into dose level 3 to ensure only 0-1 of 6 subjects have a DLT. There will be no further escalation beyond dose level 3.
- Alternatively, if 1 of the first 3 subjects within any given dose cohort experiences a DLT, an additional 3 subjects will be enrolled at that dose level. If only 1 of the total 6 subjects in a dose level experience a DLT, the study will proceed to the next dose level as planned. If 2 of the total 6 subjects in any given dose cohort experience a DLT, the next lower dose level will be explored and considered the maximum tolerated dose (MTD) if no more than 1 of 6 subjects experience a DLT. If this occurs in cohort 1, the dose will be decreased to cohort -1 and if 2 or more DLTs are reached in dose level -1, the study will be put on hold and a protocol amendment will be considered. [see Section 6.4 for "Stopping Rules"]
- The MTD for Venetoclax in combination with Gemtuzumab Ozogamicin is defined as the dose level at which fewer than 33% of subjects experience a dose limiting toxicity (DLT), and specifically is the dose level at which less than 2 out of 6 subjects experience DLT. That dose will be the recommended Phase II dose (RP2D).
- Once the RP2D has been identified, we will expand this cohort to include an additional six patients to further evaluate the efficacy and safety profile of the RP2D.

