# 5.2 Definition of Dose-limiting Toxicities

Dose-limiting toxicities (DLTs) are defined as an adverse event related (possible, probable or definite) to Venetoclax and/or Gemtuzumab Ozogamicin fulfilling one of the following criteria:

 Hematologic toxicity: treatment-related grade 3 or worse neutropenia and/or thrombocytopenia due to bone marrow hypocellularity present at the end of cycle one (day 28) with an additional 28 days allowed for count recovery (i.e. present at day 56); specifically grade 3 or worse neutropenia or thrombocytopenia with the bone marrow documented to be free of leukemic infiltration. Note: patients who enter the study with grade 3 or worse cytopenias will not be evaluable for hematologic dose-limiting toxicities.

• Non-hematologic toxicity: any grade 3 or worse treatment-related toxicity occurring within the first cycle (excluding grade 3-4 infections during cycle one).

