# NOTE: Events that can be clearly attributed to disease progression, concurrent illness or the effects of other medications will not be classified as DLTs.

DLTs will be counted based on the number of patients with a DLT at a given dose level, not the absolute number of DLTs. No single patient can trigger more than one DLT. Intra-patient dose escalation is not permitted.

Cohort	Number of Subjects	Venetoclax Daily Dose (mg)	Gemtuzumab Ozogamicin IV on Days +1, +4, +7
-1	3-6	100	
1 (start)	3-6	200	$3 \text{ mg/m}^2$
2	3-6	400	(up to one 4.5 mg vial)
3	3-6	600	

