#### 6.1 Toxicity

The NCI Common Terminology Criteria for Adverse Events (CTCAE) v5 will be used to grade adverse events. DLTs are defined in detail in section 5.2

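### Section 6.1 defines a DLT differently from the primary endpoint, and the wait for day-56 cytopenia status before escalation is only implied, misworded and absent from section 5.1

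*Combined protocol and SAP*

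**What the plan says.** **Definition.** Section 5.2, repeated in 2.2.1 and 12.2.1, makes a hematologic DLT a treatment-related grade 3 or worse neutropenia or thrombocytopenia "present at the end of cycle one (day 28) with an additional 28 days allowed for count recovery (i.e. present at day 56", with a leukemia-free marrow. It adds that "patients who enter the study with grade 3 or worse cytopenias will not be evaluable for hematologic dose-limiting toxicities". A non-hematologic DLT is "any grade 3 or worse treatment-related toxicity occurring within the first cycle (excluding grade 3-4 infections during cycle one". The note after the definition says that "DLTs will be counted based on the number of patients with a DLT at a given dose level".

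Section 6.1 opens with the statement that "DLTs are defined in detail in section 5.2". Sections 6.1.1 and 6.1.2 then each give a DLT definition of their own. The hematologic one concerns cytopenias occurring after day 56. The non-hematologic one covers the first 56 days and excludes grade 4 infections only. Section 6.3 refers to 6.1 for toxicity-related discontinuation and lists a DLT, by the definition above it, as a reason to end protocol therapy.

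**Escalation.** Section 5.1 opens level 2 "If none of the 3 subjects experience a dose limiting toxicity (DLT) during the first cycle of therapy" at level 1, and enlarges the top cohort "If all subjects in dose level 3 complete the first cycle of therapy without DLT". It has a cross-reference to 6.4. Section 6.4 monitors DLTs to day 56 and then adds, as an exception, that "if all patients in a dose cohort have recovered from DLTs prior to Day 56, dose escalation may proceed".

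**The concern.** The DLT count by dose is the whole of the primary analysis (12.6.1). It also decides whether the next patients start a higher Venetoclax dose and, through 6.3, whether a patient stays on treatment. In a multicenter trial, sites need one rule for classifying an event and one for opening the next level.

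Two things can go wrong, in opposite directions. Using 6.1.2 counts more events than 5.2, so a level is cleared less often. Using the first-cycle wording of 5.1 alone lets a level be cleared while a day-28 cytopenia could still become a DLT. The infection difference matters in practice: section 1.2.2 names pneumonia among the most common grade 3/4 events in the Venetoclax AML studies it cites.

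**Working it through.** **1. The plan's own figures.** Section 12.3 gives the upper bound (C_U + 1)/(A + B) = (1 + 1)/(3 + 3) = 0.33, which reproduces. Its 0.26 quantile is the p at which at most 1 DLT in 6 has probability one half: (1−p)^6 + 6p(1−p)^5 = 0.5 gives p = 0.264. This point disputes neither.

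**2. The two definitions side by side.**

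| Feature | 2.2.1, 5.2, 12.2.1 | 6.1.1, 6.1.2 |
|---|---|---|
| Hematologic | Present at day 28 and still at day 56 | Occurring after day 56 |
| Non-hematologic window | Cycle 1 | First 56 days |
| Infections excluded | Grade 3-4 | Grade 4 only |

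| Event judged treatment-related | 5.2 | 6.1.2 |
|---|---|---|
| Grade 3 infection in cycle 1 | Not a DLT | DLT |
| Grade 3 non-hematologic event, days 29-56 | Not a DLT | DLT |

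A cycle is 28 days (12.1), so days 29-56 can include consolidation and its two further GO doses (5.4). They need not: patients in CRi first stop Venetoclax for up to four weeks.

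**3. Timing.** A patient who is evaluable for hematologic DLT, has grade 3 or worse cytopenia at day 28 and has a leukemia-free marrow is unresolved at the end of cycle 1. That status is settled only by recovery or at day 56, so the first-cycle condition in 5.1 cannot settle it. In 6.4, a cytopenia that recovers before day 56 was never a DLT under 5.2, so recovery from DLTs is the wrong term for it.

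**4. Size of the definition conflict (all rates assumed).** A level is cleared with 0/3, or with 1/3 then 0/3:

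clear(p) = (1−p)^3 + 3p(1−p)^5.

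At p = 0.20: 0.512 + 0.197 = 0.709. If a share a of the remaining patients has an event counted only under 6.1.2, the rate becomes p′ = 1 − (1−p)(1−a).

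- a = 0.05: p′ = 1 − 0.80 × 0.95 = 0.24; clear = 0.622.
- a = 0.10: p′ = 1 − 0.80 × 0.90 = 0.28; clear = 0.536.

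**5. Size of the pending-status effect (all rates assumed; arises only if 5.1 is followed without 6.4's wait).** Take a total DLT rate p = 0.37 with independent non-hematologic (nh) and hematologic (h) components, so (1−nh)(1−h) = 0.63. With every status known, clear(0.37) = 0.360. Let m be the share of hematologic DLTs not yet known at the look. The visible rate is v = 1 − (1−nh)(1 − h(1−m)). With the first three patients' late DLTs known by the second look,

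clear = (1−v)^3 + 3v(1−p)^2(1−v)^3.

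| h | nh | m = 1 | m = 0.5 | m = 0.25 |
|---|---|---|---|---|
| 0.10 | 0.30 | 0.466 | 0.411 | 0.385 |
| 0.05 | 0.337 | 0.409 | 0.384 | 0.372 |

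For example, h = 0.10 and m = 1 give v = 0.30 and 0.343 + 3 × 0.30 × 0.3969 × 0.343 = 0.466. Against 0.360 the rises are 10.5, 5.1 and 2.5 points at h = 0.10, and 4.8, 2.4 and 1.2 points at h = 0.05.

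**The case against.** The best defence is that 5.2 governs. The same definition stands in three places, two of them statements of the primary endpoint, and 6.1 itself points to 5.2. That makes 5.2 the likelier reading. It does not remove the conflict, because 6.3 refers to 6.1 and to a DLT as previously defined, and the nearest definition above it is the one in 6.1. Nor does the 56-day window look like a slip: the next paragraph of 6.1.2 also uses day 56.

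Four stronger readings are tempting, and the documents do not support them.

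- A reader might infer that nothing makes the next level wait. Section 6.4 does imply a wait, since earlier escalation is an exception to monitoring to day 56, and 5.1 refers to 6.4.
- A reader might infer that resolved DLTs may be ignored. The counting rule in 5.2 and the next sentence of 6.4, which expands the cohort after one DLT in three, both block this.
- A reader might infer that the wrong MTD follows. A late DLT still counts toward its own level, registration is central with the dose level assigned there, and the DSMC reviews decision-rule data quarterly. A wrong MTD is possible, not automatic.
- A reader might expect a much larger pending-status effect. Assuming a 30% hematologic DLT rate with every pending case overlooked, clearance rises from 36% to 82%. A rate that high is hard to support: a hematologic DLT needs a leukemia-free marrow, patients entering with grade 3 cytopenia are not evaluable for it, and the single-agent response rates cited are 33% for GO (1.2.1) and 19% for Venetoclax (1.2.2).

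It is also fair that the infection difference applies only to events judged treatment-related, and that 1.2.2 gives no rate for pneumonia.

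**Conclusion.** The point holds as an error in the text that needs correcting. Section 6 carries a second, conflicting DLT definition that bears on discontinuation. The wait before escalation is implied in 6.4, worded in terms that do not fit 5.2, and not carried into 5.1.

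The case rests on the contradiction between sections, not on the calculated figures, whose input rates are all assumed. Under those assumptions the definition conflict is worth about 9 to 17 points of clearance probability (71% to 62% or 54%). The pending-status effect is about 1 to 11 points at hematologic DLT rates of 5% to 10%.

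**What to change.** - **6.1.1 and 6.1.2:** replace the definitions with a reference to 5.2. **6.3:** make the DLT reference point to 5.2.
- **6.4:** change recovery from DLTs to recovery from grade 3 or worse cytopenias before they meet the DLT definition, and state that any DLT counts whether or not it resolves.
- **5.1 and 6.4:** use one condition. The next level opens only when every patient in the cohort either (a) has had a DLT, or (b) has completed cycle 1 without a non-hematologic DLT and, if evaluable for hematologic DLT with grade 3 or worse cytopenia at day 28 and a leukemia-free marrow, has recovered below grade 3 or reached day 56. The existing limits on the number of DLTs then apply.

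The cost is a wording amendment with no added tests. A look may take up to four more weeks when such a cytopenia is unresolved, a wait that 6.4 already implies.

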# 7. STUDY CALENDAR & EVALUATIONS

	Screen	Induction 			Consolidation 			Maintenance Phase 		Follow up 		
	Screen		Cycl	le 1			Cycle 2	,	Cycl	es 3+	Safety F/U	Long-term Follow up
Cycle = 28 days	-28 days 	Ramp up	D1	D15	D28	D1	D15	D28	D1	D15	30 days post Tx	$\begin{array}{c} Q \ 2 \ months \\ (\pm 14 \ days)^4 \end{array}$
REQUIRED ASSESSMENTS												
Informed Consent	X											
Medical history, Prior therapy, trial awareness 	Х											
Physical exam, ECOG Performance status	Х		X	Х		Х	Х	Х	Х	C3	Х	X
Vital signs (temp, HR, BP)	Х		X	Х		Х	Х	Х	Х	C3	Х	X
Height (screening only), weight	Х		X	X		Х	X		Х	C3		X
Con meds, AEs, venetoclax drug diary review 	Х		X	Х		Х	X	Х	Х	C3	Х	X
QLQ-C30, FACT-Fatigue, walk test, chair stands		X 						Х	Q2 			X 
EKG, Echocardiogram	X											
LABORATORY ASSESSMENTS												
Pregnancy test (serum or urine) WOCBP 	-7d											
Hepatitis B/C and HIV screen	Х											
Complete Blood Cell Count with diff (CBC)	Х	X 	X 	X 	Х	X 	X 	Х	X	Х	Х	X
Basic Metabolic Panel (BMP), Uric Acid	Х	X 	X 	X 		X 	X 		Х	Х		X
Albumin, ALT, AST, bili, alk phos, T protein, LDH	Х		X 	X 		X 	X 		Х	Х		X
PT/INR PTT, fibrinogen	Х	X 	X 	X 								
DISEASE ASSESSMENT												
Bone Marrow Aspirate and Biopsy 					X			Х		C3 (if P , C13  , r		
TREATMENT EXPOSURE											•	
Gemtuzumab Ozogamicin (IV)			1,4,7			1,4						
Venetoclax (PO)		-2,-1,0		D1-28	•		D1-28	•	D1	-28		
CORRELATIVE STUDIES (SPECIMEN CO		ION)										
Buccal Swab		X 										
Whole Blood 		X 	D3 		X 			X 	C7 	, C13  , 1	relapse	
Bone Marrow Aspirate  X 					X 			X 		, C13  , 1		
BANKING SAMPLES (SPECIMEN COLLECT												
Whole Blood, Serum and Plasma 		X			X			Х	C7.	, C13, re	lapse	
FOLLOW-UP										,		
Survival status, subsequent therapy												X 

1: Screening assessment needs to be completed within 28 days. **Exception:** Bone marrow aspirate needs to be collected within 14 days prior to initiation of treatment.

2: See section 5 for treatment plan.

3: A window of  $\pm 3$  days will be applied to all cycle 1 and 2 treatment visits; a  $\pm 7$ -day window will apply for maintenance visits.

4: Subjects without documented disease progression will be followed for disease progression every 2 months ( $\pm 14$  days) for 6 months. Once disease progression is documented, subjects will enter a survival follow up period: every 2 months for 6 months from the time of documented progression.

5: Medical history will capture genetic sequencing results/cytogenetics report, prior substance abuse, organ transplant, history of liver disease and family history of cancer.

6: Drug diary review will be performed on Day 1, prior to dispensing the next cycle of venetoclax.

7: For women of childbearing potential (WOCBP): urine or serum  $\beta$ hCG, within 7 days prior to study registration. If a urine test is positive or cannot be confirmed as negative, a serum pregnancy test will be required.

8: CBC should be performed daily while subjects are in the hospital. Basic metabolic panel (calcium, carbon dioxide, chloride, creatinine, glucose, potassium, sodium, urea nitrogen), coags and uric acid measurements will be performed at least every 8 hours during the ramp up and every 8-12 hours during Cycle 1 Days 1-3 to monitor for tumor lysis syndrome. Subsequently, recommend basic metabolic panel and liver function tests be performed at least three times weekly during the induction phase. Uric acid should be evaluated at further intervals at the discretion of the investigator. Recommend measuring coags weekly during the remainder of the induction phase. During consolidation, recommend measuring these labs daily while patient is in hospital and at least weekly when outpatient, at the discretion of the treating physician. During maintenance, recommend measuring these labs at least once every two weeks when outpatient, at the discretion of the treating physician.

9: Bone Marrow Aspirate and Biopsy and/or evaluation of extramedullary site with immunophenotyping, cytochemistry, and cytogenetics (karyotype  $\pm$  FISH): to be completed at pre-treatment (within 14 days), Day 28  $\pm$  3 days during cycles 1 and 2, and  $\pm$  14 days pre-treatment cycle 7 day 1 (i.e. ~6 mo), pre-treatment cycle 13 day 1 (i.e. ~12 mo), and relapse. Patients in PR at the end of consolidation should have a repeat BM assessment after one month of maintenance.

10: Whole blood to be collected pre-treatment, Cycle 1 Day +3 ( $\pm 1$  day), end of induction, end of consolidation, pre-treatment cycle 7 day 1 (i.e.  $\sim 6$  mo), pre-treatment cycle 13 day 1 (i.e.  $\sim 12$  mo), and relapse. See section 8. See Correlative Laboratory Manual (CLM) for collection, labeling, processing, and shipping instructions.

11: Bone marrow aspirate to be collected pre-treatment, end of induction, end of consolidation, pre-treatment cycle 7 day 1 (i.e.  $\sim$ 6 mo), pre-treatment cycle 13 day 1 (i.e.  $\sim$ 12 mo), and relapse. See CLM for collection, labeling, processing, and shipping instructions. Left-over samples will be banked for potential future studies, with patient consent. See section 8.

12: Pre-treatment evaluation includes buccal swab, whole blood collection, QOL (QLQ-C30, FACT-Fatigue), walk test, and chair stands. Pre-treatment bone marrow aspirate will be collected at screening. Aspirate collection for correlative studies is required prior to therapy.

13: QOL (QLQ-C30, FACT-Fatigue), walk test and chair stands to be performed pre-treatment, at the end of consolidation, every other cycle starting with Cycle 4 and throughout long term follow up.

14: Whole Blood, Serum and Plasma for banking to be collected pre-treatment, end of induction, end of consolidation, pre-treatment cycle 7 day 1 (i.e. ~6 mo), pre-treatment cycle 13 day 1 (i.e. ~12 mo), and relapse. See CLM for collection, labeling, processing, and shipping instructions. 15: It is suggested that patients should not receive HSCT conditioning within 2-3 months of last Gemtuzumab dose and that total body irradiation (TBI)/ total marrow irradiation (TMI) as part of a HSCT conditioning regimen be avoided, if possible, per discretion of the site PI.

09JUN2022

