# Table 7. Dose Duration Reduction for Venetoclax Toxicity (Maintenance)

There will be no dose reductions of Venetoclax for hematologic toxicity during cycles 1 and 2. Patients who are in CRi after either cycle may temporarily discontinue Venetoclax for up to four weeks to allow for platelet or ANC recovery. Patients who enter the maintenance phase must have platelets  $\geq 50 \times 10^9/L$  and an ANC  $\geq 1.0 \times 10^9/L$ 

If a dose reduction is required, please follow the guidelines in Table 7. Missed Venetoclax doses are not to be made up.

Toxicity	Occurrence	Action					
Tumor Lysis Syndrome (TLS)							
TLS defined by the Cairo-Bishop criteria; see Appendix IV	Any	Implement standard TLS treatment (increase IVF). Withhold Venetoclax if TLS labs do not improve by 25% within 24 hours. Resume once TLS labs improve.					
Non-Hema	atologic Toxicities	s (Consolidation and Maintenance only)					
toxicities 2 nd and		Withhold Venetoclax. Once the toxicity has resolved to Grade 1 or baseline, resume at same dose.					
		Withhold Venetoclax. Once the toxicity has resolved to Grade 1 or baseline, resume at a reduced dosing duration (see Table 7).					
	Hematologic To	oxicities (Maintenance only)					
Grade 4 neutropenia with or without fever; or Grade 4 thrombocytopenia	1 st occurrence	Interrupt Venetoclax. To reduce infection risks associated with neutropenia, G-CSF may be administered if clinically indicated, provided there is bone marrow confirmation of leukemia clearance. Once the toxicity has resolved to Grade 2 or baseline, resume at the same dose duration (Table 7).					
	2 nd occurrence	Interrupt Venetoclax. Consider using G-CSF as clinically indicated. Once the toxicity has resolved to Grade 2 or baseline, follow dose duration reduction guidelines (Table 7).					

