#### Consider discontinuing Venetoclax if toxicities recur despite two dose duration reductions

# 6.3 **Protocol Therapy Discontinuation**

In addition to discontinuation due to therapy-related toxicities as outlined in section **6.1**, a subject will also be discontinued from protocol therapy and then followed up per protocol under the circumstances outlined below. The reason for discontinuation of protocol therapy will be documented on the electronic case report form (eCRF) and should also be discussed with the study sponsor-investigator.

- Documented disease progression
- Unacceptable toxicity
- The treating physician believes a change of therapy would be in the best interest of the subject
- Follow-up bone marrow biopsy demonstrates either significant residual leukemic blasts or significant cytoreduction with a high percentage residual leukemic blasts, but BM study is deemed by the hematopathologist to demonstrate less than a partial response.
- Bone marrow biopsy during maintenance phase shows stable disease but the treating hematologist believes that the Venetoclax is no longer of benefit.
- DLT as defined above or if there is grade 3 neutropenia or thrombocytopenia after holding Venetoclax for four weeks at the end of cycles 1 or 2
- Patient is unable to comply with protocol requirements
- The subject requests to discontinue protocol therapy, whether due to unacceptable toxicity or for other reasons. If a subject decides to prematurely discontinue protocol therapy ("refuses treatment"), the subject should be asked if he or she may still be contacted for further scheduled study assessments. The outcome of that discussion should be documented in both the medical records and in the eCRF.
- A female subject becomes pregnant
- Development of a second malignancy (except for basal cell carcinoma or squamous cell carcinoma of the skin) that requires treatment which would interfere with this study.
- If protocol therapy is interrupted for  $\geq 30$  days.
- Lost to follow up. If a research subject cannot be located to document survival, the subject may be considered "lost to follow-up." All attempts to contact the subject must be documented.

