# 12.6 Statistical Analysis Plans

# 12.6.1 Analysis Plans for Primary Objective

DLTs will be presented by dose of Venetoclax when administered with Gemtuzumab Ozogamicin.

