# Appendix IV - Cairo Bishop Guidelines

#### Cairo-Bishop definition of laboratory tumor lysis syndrome:

Either the presence of two or more of the following laboratory changes within 3 days before or seven days after cytotoxic therapy **OR** a 25% change above or below normal.

Element	Value	Change from baseline			
Uric Acid	≥476 μmol/L (8mg/dL)	or 25% increase			
Potassium	$\geq 6.0 \text{ mmol/L} (\text{or } 6\text{mEq/L})$	or 25% increase			
Phosphorus	$\geq$ 1.45 mmol/L (4.5 mg/dL) for adults	or 25% increase			
Calcium	≤1.75 mmol/L (7mg/dL)	or 25% decrease			

Adapted from the Guidelines for the management of pediatric and adult tumor lysis syndrome: an evidence-based review

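### The venetoclax TLS rule counts phosphorus, which no scheduled panel measures; Appendix IV gives two references for the 25% change, and Table 8 conflicts with the DLT rule for grade 3 or worse TLS in cycle 1

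*Combined protocol and SAP*

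**What the plan says.** **Action rule (section 6.2.2, Table 8).** The TLS row reads "TLS defined by the Cairo-Bishop criteria; see Appendix IV" and covers any occurrence. Standard TLS treatment comes first. Then: "Withhold Venetoclax if TLS labs do not improve by 25% within 24 hours. Resume once TLS labs improve". The row has no phase limit, whereas the next block of the table is restricted to consolidation and maintenance.

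**Definition (Appendix IV).** "Either the presence of two or more of the following laboratory changes within 3 days before or seven days after cytotoxic therapy". The four elements are uric acid, potassium, phosphorus and calcium. Phosphorus qualifies at or above "1.45 mmol/L (4.5 mg/dL) for adults", or on a 25% increase. The lead-in adds a 25% deviation from *normal* as an alternative. The table column that holds the 25% figures is a change from *baseline*.

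**Monitoring (section 7, footnote 8).** "Basic metabolic panel (calcium, carbon dioxide, chloride, creatinine, glucose, potassium, sodium, urea nitrogen), coags and uric acid measurements will be performed". The interval is 8 hours or shorter in ramp-up and 8 to 12 hours on Cycle 1 Days 1-3, for the stated purpose of watching for TLS. After that, the metabolic panel is recommended at least three times weekly during induction, and "Uric acid should be evaluated at further intervals at the discretion of the investigator". The calendar still marks both at Day 15.

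**DLT rule.** Section 5.2 makes any related non-hematologic toxicity of grade 3 or worse in cycle 1 a DLT and excludes only infections. Section 6.3 lists among its reasons for ending protocol therapy: "DLT as defined above or if there is grade 3 neutropenia or thrombocytopenia".

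**The concern.** A rule that decides whether venetoclax is withheld should rest on measurements that the schedule collects. Here one of the four defining analytes appears only in the appendix. A site that follows the calendar exactly has no phosphorus result, and no baseline value from which to judge a 25% increase. A site that adds phosphorus locally would ascertain TLS differently, in a multicenter trial.

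TLS is the reason section 5.4 gives for the ramp-up, and section 11.2.3 has it handled like an SAE even when it is not serious. It can also count as a DLT if it is related and grade 3 or worse in cycle 1. Under sections 5.1 and 6.4, 1 DLT in 3 patients expands a cohort and 2 in 6 send the study to the next lower dose. The primary analysis adds no further safeguard: "DLTs will be presented by dose of Venetoclax when administered with Gemtuzumab Ozogamicin". One event that is unclassified, or classified differently between sites, can therefore change an escalation decision.

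**Working it through.** No sample size, power or alpha figure bears on this point, and the plan states no number to reproduce. The check compares the passages and counts combinations.

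**1. Analytes required against analytes scheduled**

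| Appendix IV element | Footnote 8 panel and calendar rows |
|---|---|
| Uric acid | Named |
| Potassium | In the metabolic panel |
| Calcium | In the metabolic panel |
| Phosphorus | Absent |

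The other chemistry row covers albumin, ALT, AST, bilirubin, alkaline phosphatase, total protein and LDH. Alkaline phosphatase is an enzyme, not phosphorus.

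**2. Which qualifying combinations the scheduled labs can show**

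- Pairs among four analytes: C(4,2) = 6.
- Pairs without phosphorus: C(3,2) = 3 (uric acid + potassium, uric acid + calcium, potassium + calcium). The other 3 pair phosphorus with one of these analytes and cannot be seen.
- All combinations of two or more: 6 + 4 + 1 = 11. Of these, 8 still show at least two changes without phosphorus. The 3 that are lost are the phosphorus pairs.
- With phosphorus added: 6 of 6 pairs and 11 of 11 combinations.

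**3. After Cycle 1 Day 3**

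If the recommended metabolic panel is drawn but the discretionary uric acid is not, only potassium + calcium remains: C(2,2) = 1 of 6 pairs, or 4 of 11 combinations. Even that pair is recommended rather than required until the Day 15 mark. Two of the three cycle 1 gemtuzumab doses (Days 4 and 7) are still to come. If gemtuzumab is the cytotoxic therapy meant in Appendix IV, the seven-day window closes on Day 7 + 7 = Day 14. The appendix does not define the term, and venetoclax continues daily to Day 28, so the window could be read as longer.

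**4. Reference for the 25% change**

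Both references stand inside Appendix IV. As an illustration, assume a potassium baseline of 3.5 to 4.5 mmol/L and an upper limit of normal of 4.8 to 5.3 mmol/L (neither is in the documents):

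- 25% above baseline: 3.5 × 1.25 = 4.4 to 4.5 × 1.25 = 5.6 mmol/L.
- 25% above normal: 4.8 × 1.25 = 6.0 to 5.3 × 1.25 = 6.6 mmol/L.

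On these assumptions the ranges do not overlap, so one result can be TLS-positive on one reading and negative on the other. The either/or construction also leaves open whether a single analyte is enough. If it is, the pair counts in steps 2 and 3 no longer apply, but an isolated phosphorus change would still go unseen. The 25% improvement in Table 8 has no stated reference.

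**5. Resume or discontinue**

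Take a related TLS event of grade 3 or worse in cycle 1. Table 8, which applies to any occurrence, has venetoclax resume once the labs improve. Section 5.2 makes the event a DLT, and section 6.3 ends protocol therapy for a DLT. The introduction to section 6 and section 6.1.2 point to the drug sections or tables for exceptions, but neither says that TLS is exempt from the DLT rule.

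**The case against.** The strongest reply is that TLS is watched closely where the risk is expected. Three of the four analytes are drawn at least every 8 hours in ramp-up and every 8 to 12 hours through Day 3. Section 5.4 expects hospitalization throughout cycle 1. Section 5.9 recommends TLS monitoring without limiting the analytes, so sites may well measure phosphorus. This stands as far as it goes. A reader might infer that TLS will be missed or that sites cannot apply the definition, and the documents do not support that: any case with two changes among uric acid, potassium and calcium remains detectable while those are drawn. But section 5.9 names no analytes and refers to section 5.6, which is about transplant. The TLS text in section 5.7 names no laboratory tests either.

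Three other inferences also go too far. A missed TLS is not automatically a missed hold, because Table 8 withholds venetoclax only if labs fail to improve by 25% within 24 hours. Nor do the documents show TLS to be a likely cycle 1 DLT. Section 5.4 draws the concern from CLL studies. Section 1.2.2 lists febrile neutropenia, hypokalemia and pneumonia as the most common grade 3/4 events in the AML venetoclax studies (n = 74). Entry excludes WBC above 25 × 10⁹/L, and TLS prophylaxis is specified. Finally, a TLS event in ramp-up need not affect escalation: under section 12.4, a patient stopped before the first gemtuzumab dose is not evaluable for toxicity.

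On resume versus discontinue, the specific TLS row could be read as qualifying section 6.3, given the references to exceptions. That reading is possible, but no text states it. The documents also give no grade for TLS, and section 11.2.3 foresees non-serious cases, so the conflict is conditional.

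**Conclusion.** The point holds in three limited parts.

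- **Panel and definition do not match.** Phosphorus is a defining analyte and is never scheduled. Laboratory TLS that qualifies only through phosphorus, 3 of 6 qualifying pairs or 3 of 11 combinations, can go unseen on scheduled labs. Reading 3 of 6 as a 50% miss rate would be wrong, since the documents give no frequencies. After Day 3 the gap can widen, depending on what investigators choose to draw.
- **Appendix IV is ambiguous within itself** on the reference for the 25% change and on whether that change stands alone. No other section gives a competing reference.
- **Table 8 conflicts with sections 5.2 and 6.3** for related TLS of grade 3 or worse in cycle 1, and only there.

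The counts assume the rule of two or more changes and exact adherence to the calendar. How often a patient or an escalation decision would be affected cannot be estimated from the documents. The case for acting is that the gap touches both a safety rule and DLT ascertainment in cohorts of 3 to 6, and is cheap to close.

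**What to change.** 1. Align the footnote 8 panel and the calendar rows with the Appendix IV definition. One way is to add phosphorus to samples already drawn for the metabolic panel and uric acid, including a pre-treatment value so that a change from baseline can be computed.
2. Reconcile the monitoring text after Cycle 1 Day 3 with the Appendix IV window, and say which treatment starts that window.
3. In Appendix IV, state one reference for the 25% change and whether that criterion is sufficient alone. Give the reference for the 25% improvement in Table 8.
4. Reconcile the Table 8 TLS row with sections 5.2 and 6.3, so that related TLS of grade 3 or worse in cycle 1 has one DLT status and one consequence.

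The clinical rule and the monitoring schedule are the sponsor's decision. The cost is one added analyte on blood already drawn, any further analytes the sponsor chooses to schedule on draws already recommended, and wording changes.
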